• For the initial two dose levels (dose levels of 0.02 mg/kg and 0.06 mg/kg), at least one CRC patient was required. In case patients have not experienced a DLT within the first two cycles, enrollment into a higher dose level occured. In case a DLT occured, the number of patients was increased to four patients per dose level, and BLRM was performed to determine the next escalation steps. At least one Japanese patient should be included in the additional three patients that are enrolled. Then, all subsequent dose levels consisted of at least four patients. For further dose-escalation steps (dose level of 0.2 mg/kg and above), four CRC patients were required. However, in the case that only three patients were evaluable (including one Japanese patient) and none experienced a DLT as defined in Section 5.2.6.1.5 within the MTD evaluation period, then dose escalation occured based on these three evaluable patients.

If DLTs were observed in the first two consecutive patients of a previously untested dose level, subsequent enrollment to this dose cohort was stopped. The BLRM was to be re-run to confirm whether the dose level still fulfils the EWOC criterion. Based on this information, the SMC evaluated whether the next patients will be enrolled at the same dose level, or at a lower dose level.

The SMC may have recommended stopping the dose escalation phase after the criterion for MTD (Section 7.1) is fulfilled. Further patients may have been included to confirm this MTD estimate, i.e. to confirm that the EWOC criterion is still fulfilled.

The planned highest dose to be tested in the dose escalation was 4.8mg/kg based upon the pharmacodynamic modeling (refer to Figure 4.1.2.1: 1). Based on the available safety data and the BLRM, exploration of doses higher than 4.8 mg/kg was considered.

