7. STATISTICAL METHODS AND DETERMINATION OF SAMPLE SIZE

7.1 STATISTICAL DESIGN - MODEL

The trial will be performed as an open-label trial. There will be 2 parts phase Ia and Ib, which have different objectives and designs.

Phase Ia:

The primary objective of phase Ia is to determine the MTD of BI 905711 defined as the highest dose with less than 25% risk of the true DLT rate being equal or above 0.33 (EWOC criterion). Dose-escalation will be guided by a two-parameter Bayesian Logistic Regression Model (BLRM), escalating with overdose control (EWOC) (R13-4803; R13-4806).

The Bayesian logistic regression model (BLRM) is formulated as follows:

```
logit(\pi_d) = log(\alpha) + \beta*log(d/d*), where logit(\pi) = log(\pi/(1-\pi)).
```

 π_d represents the probability of having a DLT in the MTD evaluation period at dose d, d* = 3.6 mg/kg is the reference dose, allowing for the interpretation of α as the odds of a DLT at dose d*, and $\theta = (\log(\alpha), \log(\beta))$ with $\alpha, \beta > 0$ is the parameter vector of the model.

The estimated probability of a DLT at each dose level from the model will be summarized using the following intervals:

Under toxicity: [0.00, 0.16) Targeted toxicity: [0.16, 0.33) Over toxicity: [0.33, 1.00]

The BLRM-recommended dose for the next dose cohort is the dose level with the highest posterior probability of the DLT rate falling in the target interval of [0.16, 0.33) among the doses fulfilling the EWOC principle. With the EWOC criterion, it should be unlikely (i.e. posterior probability <25%) that the DLT rate at the recommended dose will exceed 0.33. However, according to the dose selection scheme in Table 4.1.2.1:1, the maximum allowable dose increment for each escalation step shall not be more than 230%.

The MTD will be considered reached if one of the following criteria is fulfilled:

• the posterior probability of the true DLT rate in the target interval [0.16, 0.33) of the MTD is above 0.5

OR

• at least 15 patients have been treated in phase Ia, of which at least 6 at the MTD.

The SMC may recommend stopping the dose escalation phase after the criterion for MTD is fulfilled.

Since a Bayesian approach is applied, a prior distribution $f(\theta)$ for the unknown parameter vector θ needs to be specified. This prior distribution used in the BLRM will be specified as a mixture of three multivariate normal distributions, i.e.

$$a(\theta) = a_1 f_1(\theta) + a_2 f_2(\theta) + a_3 f_3(\theta)$$
 with

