Scenarios 17 illustrate a case where dose level 2.4 mg/kg has probability of overdose exceeds 25%, per BLRM with the given provisional dose levels, the next optimal dose recommended would be 1.2 mg/kg. However, BLRM has flexibility to explore intermediate dose level, in both scenarios, if intermediate dose levels of 1.6 mg/kg and 1.8 mg/kg are explored, 1.6 mg/kg would be recommended as the next dose level because it has the highest probability of target dose, and overdose probability less than 25%.

Scenario 20 illustrates a case where low dose cohorts have no DLT, or 1 DLT, and the highest dose level 4.8 mg/kg has 1 DLT. In such cases, BLRM would continue to put patients on 4.8 mg/kg, but if higher dose levels are allowed, higher level e.g. 6.4 mg/kg would be recommended.

c17895778-08

E17895778-08 Clinical Trial Protocol Page 129 of 165

Proprietary confidential information © 2023 Boehringer Ingelheim International GmbH or one or more of its affiliated companies

Hypothetical data scenarios Table 10.3: 1

Scenario	Dose (mg/kg)	# Pat	# DLT	Current Dose:	Next recommended	Next reco	mmended do	se
	(8 8)			P(OD)	dose based on EWOC and escalation rule	P(UD)	P(TD)	P(OD)
1	0.02	1	0	0.033	0.06	0.885	0.068	0.047
2	0.02	1	1	0.591	NA	NA	NA	NA
2a	0.02	3	1	0.236	0.02	0.503	0.261	0.236
3	0.02	1	0					
	0.06	1	0	0.019	0.2	0.886	0.071	0.043
4	0.02	1	0					
	0.06	1	1	0.394	NA	NA	NA	NA
4a	0.02	1	0					
	0.06	3	1	0.165	0.06	0.541	0.294	0.165
5	0.02	1	0					
	0.06	4	1	0.114	0.2	0.477	0.308	0.216
6	0.02	1	0					
	0.06	1	0					
	0.2	4	0	0.005	0.6	0.913	0.069	0.018
7	0.02	1	0					
	0.06	1	0					
	0.2	4	1	0.108	0.6	0.470	0.305	0.225
8	0.02	1	0					
	0.06	1	0					
	0.2	4	2	0.374	0.06	0.421	0.374	0.205
9	0.02	1	0					
	0.06	1	0					
	0.2	4	0					0.446
	0.6	4	1	0.053	1.2	0.565	0.299	0.136
10	0.02	1	0					
	0.06	1	0					
	0.2	4	0	0.210	0.6	0.260	0.421	0.210
1.1	0.6	4	2	0.210	0.6	0.369	0.421	0.210
11	0.02	1	0					
	0.06	1	0					
	0.2 0.6	4 4	1	0.198	0.6	0.369	0.432	0.109
12		+	0	0.198	0.0	0.309	0.432	0.198
12	0.02 0.06	1 4	1					
	0.06	4	1					
	0.2	4	1	0.315	0.2	0.372	0.492	0.136
13	0.02	1	0	0.515	0.2	0.372	0.772	0.130
1 3	0.02	4	1					
	0.00	6	1					
	0.6	4	1	0.232	0.6	0.258	0.510	0.232
14	0.02	1	0	1	1000	1.200	0.010	1
	0.06	1	0					
	0.2	4	0					
	0.6	4	0					
	1.2	4	1	0.025	2.4	0.584	0.279	0.138

Page 130 of 165

Proprietary confidential information © 2023 Boehringer Ingelheim International GmbH or one or more of its affiliated companies

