Scenarios 4 and 5 (very low-toxicity scenario) shows, that when the true DLT rate is very low, i.e. the majority dose levels with true DLT rate below the target interval, then more likely the model will declare a underdose as MTD. Since in scenario 4 none of the dose levels has an assumed true toxicity rate in the target interval, none of the simulated trials has declared a MTD with true DLT rate in the target dose range. In scenario 5 only few dose level was assumed to have true DLT rate in the target range, but at the upper end of the target range, therefore only a low number of simulated trials declared MTD at this dose with true DLT rate in the target range. The probability of observing a DLT at 1.2mg/kg is 0.13 and therefore close to the lower bound of the target interval. Adding up the corresponding probability of declaring this dose as an MTD (35.8% leads to a target rate of 83.2). Both scenarios have a very low percentage of trials stopped since no MTD was reached (either because the maximum number of patients was reached before declaring MTD or because too many DLTs were simulated to continue escalation).

In Scenarios 6 and 7, dose-toxicity relationship is non-monotonic. Scenarios 6 and 7 illustrates that the majority simulated trials (over 70%) declare the target dose levels as MTD.

The mean patient numbers across different scenarios is around 28, though the maximum can go up to 52 during simulation. This shows that the planned maximum of 40 patients is reasonable for phase Ia.

In summary, the considered data scenarios show a reasonable behaviour of the model and the operating characteristics demonstrate a good precision of MTD determination.

C17895778-08 Clinical Trial Protocol Page 133 of 165

Proprietary confidential information © 2023 Boehringer Ingelheim International GmbH or one or more of its affiliated companies

DESCRIPTION OF GLOBAL AMENDMENT(S) 11.

11.1 **GLOBAL AMENDMENT 1**

Date of amendment	10Dec2019		
EudraCT number	2018-003268-29		
EU number	2018-003208-29		
BI Trial number	1412-0001		
BI Investigational Medicinal	BI 905711		
Product(s)			
Title of protocol	A first-in-human phase Ia/b, open lab		
	multicentre, dose escalation study o		
	in patients with advanced gastrointes	tinal cancers	
Global Amendment due to urgent sa	fety reasons		

Global Amendment		X	
Section to be changed	Synopsis		
Description of change	Revised to clarify Exclusion #1		
Rationale for change	Revision to align description of Excl	usion #1 with	

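### The first MTD-reached criterion sets no minimum number of patients at the dose, and Appendix 10.3 does not state which MTD rule produced Table 10.3:3

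*Protocol*

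**What the plan says.** CTP 7.1 introduces the rule with "The MTD will be considered reached if one of the following criteria is fulfilled". The two criteria are joined by OR:

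- Criterion 1: "the posterior probability of the true DLT rate in the target interval [0.16, 0.33) of the MTD is above 0.5".
- Criterion 2: "at least 15 patients have been treated in phase Ia, of which at least 6 at the MTD".

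The consequence is permissive: "The SMC may recommend stopping the dose escalation phase after the criterion for MTD is fulfilled". CTP 3.1.1.3 adds that "Further patients may have been included to confirm this MTD estimate", which is optional and gives no number. SAP 7.4.1 refits the BLRM and reports posterior summaries and overdose-control status by dose. It adds no minimum.

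In its hypothetical data scenarios, Appendix 10.3 uses the target probability to choose the next cohort's dose. On scenario 17 it says that "1.6 mg/kg would be recommended as the next dose level because it has the highest probability of target dose".

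Appendix 10.3 simulates seven true dose-toxicity curves and concludes that "the operating characteristics demonstrate a good precision of MTD determination". It gives the cohort size (4) and the number of trials (1000 per scenario), but not the MTD rule that was programmed. CTP 7.7 relies on these simulations for its expectation of 20-36 evaluable patients.

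**The concern.** The 6-patient minimum in criterion 2 ensures that an MTD rests on more than one cohort of four. Because of the OR, criterion 1 bypasses it: a two-parameter model can place more than half its posterior mass in the target interval by borrowing from other doses.

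The MTD is a Phase Ia primary endpoint, and CTP 3.1.2 and 4.1.2.2 make it an upper limit for the Phase Ib doses. If Table 10.3:3 came from a rule other than the one written in 7.1, its claims about precision and sample size do not describe the written design.

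**Working it through.** **Scenario 13 (Table 10.3:1).** Patients by dose: 1 at 0.02, 4 at 0.06, 6 at 0.2 and 4 at 0.6 mg/kg, so 1 + 4 + 6 + 4 = 15. Printed values at 0.6 mg/kg: P(UD) 0.258, P(TD) 0.510, P(OD) 0.232.

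- Overdose control: 0.232 < 0.25, met.
- Criterion 1: 0.510 > 0.5, met.
- Criterion 2: 15 ≥ 15, met; 4 ≥ 6, not met.

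Criterion 2 fails only on the 6-patient minimum, yet by criterion 1 the MTD is reached. Recomputing with logit(π_d) = log(α) + β·log(d/3.6), the three-component prior of Table 7.1:1 and a binomial likelihood gives P(TD) 0.512 and P(OD) 0.227, so the example is sound.

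**Table 10.3:3.** Inputs: the same prior, the true rates of Table 10.3:2, cohorts of 4, start at 0.02 mg/kg and at most 52 patients. Assumed, because the Appendix does not say: the next dose is the one with the highest P(TD) among doses with P(OD) < 0.25, at most one level up, and the extra level in scenario 4 is left out. There were 8000 trials per scenario. Three MTD rules were tried:

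- A: 7.1 as written, applied to any recommended dose.
- B: the same OR rule, but only when the recommended dose is the dose just given.
- C: as B, with at least 6 patients at the dose AND (P(TD) > 0.5 OR at least 15 in total).

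Mean patients per trial (difference from the table), with the share of trials declaring an MTD on fewer than 6 patients:

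| Scenario | Table 10.3:3 | A | A, <6 | B | B, <6 | C |
|---|---|---|---|---|---|---|
| 1 | 29.8 | 26.0 (-3.8) | 37% | 28.2 (-1.6) | 17% | 29.7 (-0.1) |
| 2 | 19.5 | 16.2 (-3.3) | 32% | 18.6 (-0.9) | 5% | 19.1 (-0.4) |
| 3 | 33.3 | 32.8 (-0.5) | 18% | 34.1 (+0.8) | 9% | 34.6 (+1.3) |
| 4 | 35.7 | 36.1 (+0.4) | 2% | 36.2 (+0.5) | 1% | 36.3 (+0.6) |
| 5 | 33.9 | 29.9 (-4.0) | 40% | 32.6 (-1.3) | 11% | 33.6 (-0.3) |
| 6 | 28.1 | 24.9 (-3.2) | 34% | 27.3 (-0.8) | 10% | 28.2 (+0.1) |
| 7 | 28.0 | 25.0 (-3.0) | 30% | 27.6 (-0.4) | 7% | 28.1 (+0.1) |
| Root mean square difference | | 2.96 | | 0.99 | | 0.58 |

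Repeat runs put the upper end of the fewer-than-6 share at about 45% under A and 18% under B. The largest trial under A is 36-44 patients across scenarios in one run and 36-48 in the 8000-trial run. The table prints 48-52; B and C both reach 52.

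**What the fit can show.** A does not match the table. B and C both stay within 2 patients of every printed mean. The 6-patient minimum without the dose-just-given limit has a root mean square difference of 1.21, slightly worse than B. Another rule with no minimum at the dose (P(TD) > 0.5 and at least 15 patients in total, or criterion 2; dose just given; highest dose passing overdose control chosen) gives 0.59, level with C. The printed means therefore do not identify the coded rule.

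**The case against.** **The match to a 6-patient minimum proves nothing.** A reader might infer that Table 10.3:3 can be reproduced only if at least 6 patients at the MTD are required. The documents do not support that: rule B has no such minimum and comes close in all seven scenarios. In scenarios 3 and 4 rule A is nearer to the printed means than C. This objection stands. What remains is that 7.1 applied to any recommended dose does not reproduce the table, that B and C each add a condition 7.1 does not state, and that the Appendix names no rule.

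**Scenario 17 is not an MTD on no patients.** A reader might infer that it is, since 1.6 mg/kg is untreated and has a printed P(TD) of 0.517. But the Appendix presents 1.6 mg/kg as an optional intermediate next dose, with the choice left to the SMC. At the provisional dose of 1.2 mg/kg P(TD) is 0.454, and recomputation at 1.6 mg/kg gives 0.499, on the threshold. This objection stands.

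**Reaching the criterion is a stopping trigger, not the endpoint.** The endpoint in CTP 2.1.2 is the highest dose passing the overdose limit. The SMC need not stop and may add patients. That softens the practical effect. It does not supply a minimum, and Table 10.3:3 reports how often trials declare an MTD, which depends on the rule.

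**Back-fill patients add data.** The BLRM also uses non-CRC patients, up to 4 per level from level 3, and the Appendix says it models CRC patients only. But CTP 3.1.1.2 places back-fill one level below the dose under study, so it does not guarantee more patients at the dose just tested.

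**It is too late to matter.** CTP 1.2 reports no DLT and no MTD, Phase Ia recruitment is complete, and the programme is ending. No past decision changes, but the BLRM re-run after expansion (CTP 2.1.2 and 3.1.2) remains in the plan.

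**Conclusion.** The point holds in limited form. Criterion 1 has no minimum at the dose, no other section supplies one, and scenario 13 meets it on one cohort of four. The rule behind Table 10.3:3 is unstated. Applied to any recommended dose, the written rule gives 3.0 to 4.0 fewer patients in scenarios 1, 2, 5, 6 and 7, and its mean counts span about 16-36 where CTP 7.7 quotes 20-36. These sizes rest on the assumed next-dose rule.

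The gain in accuracy from a minimum is modest. Adding it to rule A moves in-target MTDs from 62% to 67% in scenario 2 and from 50% to 55% in scenario 5, and overdose MTDs in scenario 5 from 11% to 8%. In scenario 1 in-target MTDs move from 62% to 64%, and scenarios 6 and 7 do not improve. Under the dose-just-given limit (B to C) the differences are smaller still. The main benefit is that any MTD statement rests on a stated amount of data and that text and table describe the same rule.

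A reader might also infer that the Phase Ia conclusion is unsafe. It is not affected: with no DLT, criterion 1 did not come into play. The effect is confined to the text of 7.1, Table 10.3:3 and any later MTD statement.

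**What to change.** 1. In CTP 7.1, apply the minimum to both criteria: MTD reached if at least 6 evaluable patients were treated at that dose AND (posterior target probability above 0.5 OR at least 15 patients treated in total). Criterion 2 is unchanged by this.
2. Use the same rule for any MTD statement under SAP 7.4.1 or from the BLRM re-run after expansion.
3. State in Appendix 10.3 the MTD and next-dose rules actually coded for Table 10.3:3. If the OR rule was coded, rerun the table under the amended rule and print the result.

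The text cost is one clause and one or two sentences. For patients, moving from A to C adds 3.7, 2.9, 1.8, 0.2, 3.7, 3.3 and 3.1 on average in scenarios 1-7 (column C minus column A), so about 2-4 outside scenario 4. If the dose-just-given limit was already intended (B to C), it adds 0.1 to 1.5. In most scenarios this is already within the printed patient numbers: C exceeds the printed mean by at most 1.3 (scenario 3).

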2: High Tox	0.100	0.221	0.305	0.356	0.408	0.454	0.486	0.498
3: Low Tox	0.009	0.018	0.057	0.100	0.122	0.160	0.174	0.180
4: Very low Tox*	0.001	0.008	0.010	0.020	0.050	0.065	0.080	0.100
5: Non-Logis-tic	0.020	0.050	0.065	0.090	0.130	0.250	0.321	0.508
6: Non-Monotonic 1	0.020	0.080	0.120	0.202	0.250	0.389	0.250	0.202
7: Non-Monotonic 2	0.010	0.050	0.090	0.210	0.327	0.389	0.327	0.210

^{*} Additional dose level 300mg added (assumed true tox probability of 0.789) to allow R code to run

For each of these scenarios, 1000 trials were simulated. 4 patients per dose cohort were assumed as default cohort size for the simulations. It was then assessed how often a dose was declared as MTD with true DLT rate in the under-, targeted or over-dose range. Furthermore, the average, minimum and maximum number of patients per trial and the average number of DLTs per trial are reported. Results are shown in Table 10.3: 3.

Proprietary confidential information © 2023 Boehringer Ingelheim International GmbH or one or more of its affiliated companies

Table 10.3: 3 Simulated operating characteristics

Scenario	% of trials rate in	declaring an l	# Patients	# DLT		
	underdose	target dose	overdose	stopped	Mean (Min-Max)	Mean (Min- Max)
1	31.6	62.7	0.0	5.7	29.8 (4 - 52)	4.6 (1 - 13)
2	4.6	63.9	16.1	15.4	19.5 (4 - 48)	4.6 (2 - 13)
3	20.9	78.4	0.0	0.7	33.3 (8 - 52)	3.4 (0 -11)
4	98.3	0.0	0.0	1.7	35.7 (12 - 52)	2.1 (0 - 7)
5	45.8	47.4	5.6	1.2	33.9 (4 - 52)	5.3 (1 - 13)
6	21.5	72.9	5.0	0.6	28.1 (4 - 52)	4.5 (1 - 14)
7	17.4	78.2	4.2	0.2	28.0 (8 - 52)	4.7 (1 - 12)

^{*1} trial declared the additional dose 300mg/kg as MTD

In Scenario 1, which reflects the case that the true dose-toxicity is aligned with prior means, 62.7% of the simulated trials declared a dose as MTD with true DLT rate in the targeted dose range.

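### Appendix 10.3 labels 83.2% a target rate for scenario 5 by adding trials that select a dose the protocol defines as under-dosing; the reported in-target rate is 47.4%

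*Protocol*

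**What the plan says.** Protocol Section 7.1 fixes three intervals for the true DLT rate: "Under toxicity: [0.00, 0.16) Targeted toxicity: [0.16, 0.33) Over toxicity: [0.33, 1.00". SAP Section 7.4.1 keeps them for the final BLRM analysis and calls the lowest one under dosing.

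Appendix 10.3 simulates seven dose-toxicity curves ("For each of these scenarios, 1000 trials were simulated") and classifies each declared MTD by its true DLT rate. For scenario 5, Table 10.3: 2 gives the true rates from 0.02 to 4.8 mg/kg as "5: Non-Logis-tic 0.020 0.050 0.065 0.090 0.130 0.250 0.321 0.508". Table 10.3: 3 gives the result as "5 45.8 47.4 5.6 1.2 33.9 (4 - 52) 5.3 (1 - 13"; the first four numbers after the scenario label are the percentages under-dose, target dose, over-dose and stopped.

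The text below Table 10.3: 3 groups scenario 5 with scenario 4 under a heading of very low toxicity. It says that the few in-target doses of scenario 5 lie towards the top of the target range, and that few trials therefore chose one. It continues: "The probability of observing a DLT at 1.2mg/kg is 0.13 and therefore close to the lower bound of the target interval". Then comes the sentence at issue: "Adding up the corresponding probability of declaring this dose as an MTD (35.8% leads to a target rate of 83.2". The appendix closes by saying that "the operating characteristics demonstrate a good precision of MTD determination".

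**The concern.** A rate called the target rate should count only trials that choose a dose inside the target interval. At 0.13, 1.2 mg/kg is outside it. The text therefore attaches the label to a quantity that differs from the one Table 10.3: 3 reports under the same name, and the difference is large.

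Scenario 5 has the lowest in-target share of the six scenarios that contain a target dose. Read as a target rate, 83.2% would make it the best of the seven, above the 78.4% of scenario 3. A reader relying on the text could accept the closing claim of good precision without seeing that, in this scenario, under-dose selection is almost as frequent as target selection.

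**Working it through.** **Inputs.** Intervals from protocol Section 7.1; true rates from Table 10.3: 2; outcome percentages from Table 10.3: 3; the 35.8% and 83.2 from the text of Appendix 10.3; 1000 simulated trials per scenario.

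**1. Reproduce the stated figure.** 47.4 + 35.8 = 83.2. The addition is right.

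**2. Classify the scenario 5 doses.**

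| Dose (mg/kg) | True DLT rate | Class under Section 7.1 |
|---|---|---|
| 0.02 to 0.6 | 0.020 to 0.090 | under |
| 1.2 | 0.130 | under (0.030 below the bound) |
| 2.4 | 0.250 | target |
| 3.6 | 0.321 | target |
| 4.8 | 0.508 | over |

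**3. Locate the 35.8%.** The table row sums to 45.8 + 47.4 + 5.6 + 1.2 = 100.0. The trials choosing 1.2 mg/kg therefore sit in the underdose column. They are 35.8 / 45.8 = 78% of it and leave 45.8 - 35.8 = 10.0% for the lower doses.

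**4. In-target rate on the protocol's definition.** 47.4%. Among trials that declared an MTD at all it is 47.4 / (100 - 1.2) = 48.0%.

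**5. Simulation error.** SE = sqrt(0.474 x 0.526 / 1000) = 0.0158, so the 95% interval is 0.474 +/- 1.96 x 0.0158, or 44.3% to 50.5%.

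**6. Is the near-miss credit applied elsewhere?** No. In scenario 1, 0.6 mg/kg has a true rate of 0.149, only 0.160 - 0.149 = 0.011 below the bound. That is closer than 0.13, and it gets no credit.

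**7. The description of scenario 5.** The midpoint of the target interval is (0.16 + 0.33) / 2 = 0.245, so 2.4 mg/kg at 0.250 is near the middle; only 3.6 mg/kg at 0.321 is near the top. The three highest doses have rates of 0.250, 0.321 and 0.508, which is not very low toxicity. It is true that five of the eight doses are below 0.16.

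**8. The summary across scenarios.** In-target shares are 62.7, 63.9, 78.4, 72.9 and 78.2% in scenarios 1, 2, 3, 6 and 7, and 47.4% in scenario 5. Scenario 4 has no provisional dose in the target interval and shows 0.0%.

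**9. Scenario 4.** The footnote to Table 10.3: 3 says that one "trial declared the additional dose 300mg/kg as MTD". Table 10.3: 2 adds that dose to scenario 4 with an assumed rate of 0.789, an over-dose. One trial in 1000 is 0.1%, but the row reads 98.3 + 0.0 + 0.0 + 1.7 = 100.0 and has no place for it.

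**The case against.** The strongest reply is that nothing is concealed. Table 10.3: 3 prints 47.4% unaltered. The text says that an under-dose is the more likely declaration in scenarios 4 and 5, gives the 0.13, gives the reason for adding 1.2 mg/kg, and states the 35.8%. A reader can undo the step. This stands, and it limits the point to a wrong label.

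Three stronger readings are tempting and are not supported.

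- A reader might infer that the outcomes now total 45.8 + 83.2 + 5.6 + 1.2 = 135.8%. The protocol never reports that combination. Moving 1.2 mg/kg out of the underdose column gives 10.0 + 83.2 + 5.6 + 1.2 = 100.0.
- A reader might infer that scenario 5 is the only monotone test of a curve the model does not fit. It is the only one labelled non-logistic. However, Section 7.1 makes the logit linear in log dose, and scenario 4 departs from its best-fitting straight line about as much (root mean square residual 0.33 against 0.34 on the logit scale). Scenarios 2 and 3 are not straight either, yet reach 63.9% and 78.4% in target.
- A reader might say that the design is shown to hit the target in fewer than half of trials. The estimate is below half, but its 95% interval reaches 50.5%.

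It can also be said that a true rate of 0.13 is a mild miss. That is a fair reason to report the 35.8% separately, but not to call it target. Finally, the practical weight is small, and this stands: the protocol reports that phase Ia recruitment is complete, that no DLT occurred in 48 patients and that no MTD was reached. SAP Section 7.4.1 uses the prior and the intervals, not this figure.

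**Conclusion.** The point holds as a labelling error. By the protocol's definition the reported scenario 5 target rate is 47.4%, against 45.8% under-dose and 5.6% over-dose; 83.2% is the share choosing a target dose or 1.2 mg/kg. The label overstates the target rate by 35.8 percentage points. The accompanying description of scenario 5 is inaccurate for 2.4 mg/kg and for the overall toxicity level, and the closing statement on precision needs a qualification for this scenario. The scenario 4 row and its footnote disagree by one trial.

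The conclusion rests on taking the tabulated simulation output as given. The simulation code is not in the documents and its rules are not fully specified. Approximate re-simulation under several readings of the stopping and escalation rules gave about 54% to 60% in target and 24% to 32% at 1.2 mg/kg. That does not show the table to be wrong, but it is a reason to cite 47.4% as the protocol's reported rate and not as an independently confirmed one.

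**What to change.** In Appendix 10.3:

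- State 47.4% as the scenario 5 target rate. If 83.2% is kept, label it as target dose or 1.2 mg/kg (true rate 0.13, under-dosing by definition).
- Describe scenario 5 as a non-logistic curve with five of eight doses below the target interval, one target dose near its middle (0.250) and one near its top (0.321).
- Qualify the summary: 63% to 78% in target in scenarios 1, 2, 3, 6 and 7, but 47.4% against 45.8% under-dose in scenario 5, with no target dose available among the provisional doses in scenario 4.
- Reconcile the scenario 4 row with its footnote from the simulation output. Changing only the over-dose entry to 0.1% would make the row sum to 100.1%, so the output must show which other cell falls.

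A tolerance applied equally on both sides of the target interval is not needed. The overdose-control rule deliberately treats the two sides differently, so a symmetric allowance would be a matter of preference.

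The cost is a wording change and one less favourable figure. No new simulation is required. Because the protocol is at its final stage, a correcting note where these operating characteristics are next cited, such as the trial report, would serve the same purpose.
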